5.2 Study duration

Phase I: Patients will remain on study for six 28-day cycles or until criteria for discontinuation (7.6.1) are met, whichever comes earlier. Decisions on subsequent maintenance therapy will at the discretion of the treating physician. If the patient's myeloma is controlled in at least stable disease panobinostat may be continued free of charge to the patient. Follow up after completion of cycle 6 is at the discretion of the treating physician but if panobinostat is continued, monitoring for electrolyte abnormalities, especially potassium and magnesium, at a frequency appropriate for the respective patient, is recommended. This protocol may be amended to

include a formal maintenance phase and/or a phase II portion after review of safety and preliminary efficacy data.

Phase II: Patients will receive therapy according to DL2 and will remain on study until criteria for discontinuation (7.6.1) are met.

5.3 Dose levels

Dose levels are defined in table Table 5-1

Dose level	PO Panobinostat	PO MLN9708 (Ixazomib)	PO Dexamethasone
1	20mg d 1,3,5,15,17,19 q 28 d	3mg d1,8,15 q 28 d	20mg d 1,2,8,9,15,16 q 28 d
2	20mg d 1,3,5,15,17,19 q 28 d	4mg d1,8,15 q 28 d	20mg d 1,2,8,9,15,16 q 28 d

5.4 Dose limiting toxicity

Dose limiting toxicity (DLT) will be assessed during the first cycle and be defined as the following drug-related adverse events according to CTCAE version 4.03 (if an adverse event is attributed to progressive disease, it will not be counted as DLT):

- Grade 4 or higher neutropenia or thrombocytopenia that does not resolve to grade 3 or lower within 7 days after detection while MLN9708 (ixazomib) and panobinostat are held.
- Use of G-CSF or platelet transfusions in cycle one
- Neutropenic fever (with grade 3 or grade 4 neutropenia)
- QTcF increase to ≥ 480 msec that persists ≥ 7 days after withholding panobinostat and MLN9708
- Any grade 3 or higher non-hematologic adverse events except:
 - Nausea, vomiting, diarrhea, or electrolyte abnormalities that can be reduced to grade 2 with supportive measures within 7 days

Patients who cannot be assessed for DLT due to progressive disease or other reasons will be replaced. Patients who develop a DLT may remain on study.

6 Study population

Patients with relapsed or refractory myeloma after at least two previous regimens including a proteasome inhibitor and an IMiD™ seen at the Cleveland Clinic Taussig Cancer Center will be screened for enrollment. Approximately 700 patients with multiple myeloma are seen each year at this site and approximately 600 have relapsed or refractory myeloma. The study will be offered to our partner institution within the Case Comprehensive Cancer Center, the Seidman Cancer Center of University Hospitals and Case Western University, where approximately 100 patients with relapsed or refractory multiple myeloma are seen each year. Participation is expected and would not alter per patient costs. We have accrued 11 patients to phase I in about 12 months and expect to enroll to phase II at a faster pace since no interruptions for DLT assessments will be required. We anticipate it will take about 18 months to accrue additional 20 patients to phase II. .

6.1.1 Patient population

Eleven patients have been enrolled to phase I and an additional 20 patients are planned for phase two totaling 31 patients for the entire study.

6.1.2 Inclusion and exclusion criteria

Patients must have baseline evaluations performed prior to the first dose of study drug and must meet all inclusion and exclusion criteria. Results of all baseline evaluations, which assure that all inclusion and exclusion criteria have been satisfied, must be reviewed by the Principal Investigator prior to enrollment of that patient. In addition, the patient must be thoroughly informed about all aspects of the study, including the study visit schedule and required evaluations and all regulatory requirements for informed consent. The written informed consent must be obtained from the patient prior to enrollment. The following criteria apply to all patients enrolled onto the study unless otherwise specified.

Inclusion criteria

1. Male or female patients aged ≥ 18 years old
2. Ability to provide written informed consent obtained prior to participation in the study and any related procedures being performed
3. Patients must carry a diagnosis of symptomatic multiple myeloma according to international myeloma working group criteria⁵⁰ and have relapsed or refractory disease according to international uniform response criteria and must have previously received therapy with a proteasome inhibitor and an IMiD™^{51,52}(see also 6.2).
4. Must have measurable disease defined as any of the following: Serum m-spike ≥ 1 g/dL, 24 h urine m-spike of at least 200mg/d, involved serum free light chains ≥ 100 mg/L with abnormal serum free light chain ratio, bone marrow plasma cells of at least 30%
5. ECOG PS ≤ 2
6. No gastro-intestinal condition, that in the opinion of the treating physician or the principal investigator significantly limits oral absorption
7. No serious uncontrolled coexisting medical condition

8. Patients must meet the following laboratory criteria:
 - $ANC \geq 1.0 \times 10^9/L$ without use of pegfilgrastim in the preceding 21 days and without non-pegylated G-CSF or GM-CSF within 7 days prior to study entry
 - Hemoglobin ≥ 8 g/dl (may be after transfusion of packed red blood cells or use of erythropoiesis stimulating agents)
 - Platelets $\geq 70 \times 10^9/L$ without platelet transfusion 7 days prior to study entry
 - AST and ALT $\leq 2.5 \times$ ULN
 - Serum bilirubin $\leq 1.5 \times$ ULN
 - Serum potassium \geq LLN and serum magnesium \geq LLN (electrolyte levels may be achieved with repletion or other supportive medications like potassium sparing diuretics) Creatinine clearance ≥ 30 mL/min according to Cockcroft-Gault formula (see Section 22)
 - Clinically euthyroid. Note: Patients are permitted to receive thyroid hormone supplements to treat underlying hypothyroidism.
9. Baseline MUGA or ECHO must demonstrate LVEF $\geq 45\%$
10. Women of childbearing potential (WOCBP) must have a negative serum pregnancy test within 7 days prior to start of study treatment
11. Male patients, even if surgically sterilized (i.e., status post vasectomy), have to either:
 - Agree to practice effective barrier contraception during the entire study treatment period and through 4 months after the last dose of study treatment, OR
 - Must also adhere to the guidelines of any treatment-specific pregnancy prevention program, if applicable, OR
 - Agree to practice true abstinence when this is in line with the preferred and usual lifestyle of the subject. (Periodic abstinence [e.g., calendar, ovulation, symptothermal, post-ovulation methods] and withdrawal are not acceptable methods of contraception.
12. Female patients have to fulfill one of the following:
 - Be postmenopausal for at least 1 year before the Screening visit, OR
 - Be surgically sterile, OR
 - If of childbearing potential, agree to practice 2 effective methods of contraception, at the same time, from the time of signing the informed consent through 90 days after the last dose of study treatment
 - Oral contraceptives are generally metabolized by CYP3A4. Since the induction potential of panobinostat to induce CYP3A4 is unknown, patients who are using oral contraceptives as a method of contraception, and are sexually active, should use another effective contraceptive method, AND Must also adhere to the guidelines of any treatment-specific pregnancy prevention program, if applicable, OR

- Agree to practice true abstinence when this is in line with the preferred and usual lifestyle of the subject. (Periodic abstinence [e.g., calendar, ovulation, symptothermal, post-ovulation methods] and withdrawal are not acceptable methods of contraception.)
13. At least 7 days must have passed since the last treatment with lenalidomide, pomalidomide, thalidomide, proteasome inhibitors, or low dose cyclophosphamide (up to 50mg daily), at least 21 days must have passed since the last treatment with daratumumab, elotuzumab, investigational therapy and most conventional chemotherapy including cyclophosphamide above 50mg per dose, bendamustine, doxorubicin, cisplatin, and etoposide; and at least 35 days since the last treatment with melphalan.

Exclusion criteria

1. Prior anti-cancer treatment with MLN9708 (ixazomib), HDAC, DAC, HSP90 inhibitors or valproic acid
2. Prior participation in a randomized controlled study that included MLN9708 (ixazomib) in one of the treatment arms independent of whether assigned to MLN9708 (ixazomib) or not
3. Patients who will need valproic acid for any medical condition during the study or within 5 days prior to first panobinostat treatment
4. Female patients who are lactating or have a positive serum pregnancy test during the screening period.
5. Impaired cardiac function or clinically significant cardiac diseases, including any one of the following:
 - History or presence of sustained ventricular tachyarrhythmia. (Patients with a history of atrial arrhythmia are eligible)
 - Any history of ventricular fibrillation or torsade de pointes
 - Bradycardia defined as $HR < 50$ bpm. Patients with pacemakers are eligible if $HR \geq 50$ bpm.
 - Screening ECG with a $QTcF > 470$ msec ($QTcF = QT/\sqrt{RR}$). If potassium or magnesium blood levels are below normal limits, consider repeating ECG after correction of these electrolytes.
 - Right bundle branch block + left anterior hemiblock (bifascicular block)
 - Patients with myocardial infarction or unstable angina ≤ 6 months prior to starting study drug
 - Other clinically significant heart disease (e.g., CHF NY Heart Association class III or IV, uncontrolled hypertension, history of labile hypertension, or history of poor compliance with an antihypertensive regimen)
6. Impairment of GI function or GI disease that may significantly alter the swallowing absorption of panobinostat and MLN9708

7. Patients with diarrhea > CTCAE (version 4.03) grade 2
8. Patient has \geq Grade 3 peripheral neuropathy, or \geq Grade 2 with pain on clinical examination during the screening period.
9. Patients with known metastasis of malignant plasma cells to the central nervous system (if not suspected no specific testing is required)
10. Other concurrent severe and/or uncontrolled medical conditions (e.g., uncontrolled diabetes or active or uncontrolled infection) including abnormal laboratory values, that could cause unacceptable safety risks or compromise compliance with the protocol
11. Patients using medications that have a relative risk of prolonging the QT interval or inducing torsade de pointes if treatment cannot be discontinued or switched to a different medication prior to starting study drug. If an alternative medication that does not risk QT prolongation can safely be used in the opinion of the treating physician and the treatment is changed to that medication, the patient may be enrolled.
12. Patients who have not passed the nadir of bone marrow suppression from previous anti-myeloma therapy yet. If in doubt, serial CBCs with differential should be obtained.
13. The corticosteroids prednisone and dexamethasone may be continued until the day before treatment start if all related adverse events are controlled at CTCAE version.4.03 grade \leq 1.
14. Patients who have received radiation therapy to more than half of the pelvis or more than half of the spine within \leq 2 weeks prior to starting study treatment; or who have not yet recovered from side effects of such therapies.
15. Patients who have undergone major surgery \leq 4 weeks prior to starting study drug or who have not recovered from side effects of such therapy
16. Systemic treatment, within 14 days before study enrollment, with strong inhibitors of CYP1A2 (fluvoxamine, enoxacin, ciprofloxacin), strong inhibitors of CYP3A (clarithromycin, telithromycin, itraconazole, voriconazole, ketoconazole, nefazodone, posaconazole) or strong CYP3A inducers (rifampin, rifapentine, rifabutin, carbamazepine, phenytoin, phenobarbital), or use of Ginkgo biloba or St. John's wort.
17. Ongoing or active systemic infection, known human immunodeficiency virus (HIV) positive, known active hepatitis B virus hepatitis, or known active hepatitis C virus hepatitis.
18. Concurrent diagnosis of another malignancy if either systemic treatment or surgery is expected to be required within 2 years from study entry.
19. Known allergy to any of the study medications, their analogues, or excipients in the various formulations of any agent.
20. Patients with any significant history of non-compliance to medical regimens or unwilling or unable to comply with the instructions given to him/her by the study staff.
21. Infection requiring systemic antibiotic therapy or other serious infection within 14 days before study enrollment unless the patient is felt to have fully recovered and any antibiotics that are continued are either beta lactam antibiotics or are specifically allowed on study according to 7.7.1

22. Participation in other clinical trials, including those with other investigational agents not included in this trial, within 21 days of the start of this trial and throughout the duration of this trial.

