7.5.4 Dose modifications for prolonged QTcF

All cardiac events should be treated as per the local standard of care and referred to a specialist if clinically indicated. Initial assessments will be made by the treating physician based on the QTc calculated by the ECG machine according to the Bazett formula ($QTcB = QT/\sqrt{RR}$). Any panobinostat dosing or withholding decisions will only be made after calculation of the QTcF according to the following formula $QTcF = QT/\sqrt[3]{RR}$ by trained research nurses or the principal investigator. If a patient cannot be dosed due to prolonged QTcF for more than 7 days since last dose, patient should be discontinued from study.

Table 7-5 Dose modifications for prolonged QTcF

ECGs to be performed at specified time point	Abnormality Noted	Dose Modification Guideline - At any time during a cycle of therapy (including intended day of dosing)
Dose modifications are based on local readings of the average QTcF* of triplicate ECGs. *QTcF: Heart rate corrected QT interval using the Fredericia formula: $QTcF = QT (msec) / \sqrt[3]{RR} (sec)$		
Pre-panobinostat-dose on cycle 1, day 1: 3 ECGs separated by 5-10 minutes, obtained prior to panobinostat dosing.	Average QTcF > 470 msec	
Check and correct the patient's serum potassium, magnesium, and calcium immediately, as well as evaluate con-meds that can prolong (or is known to be associated with) QTc interval.
 
Repeat 3 pre-panobinostat-dose ECGs. If the 3 pre-panobinostat-dose ECGs: Do not meet criteria again, discontinue patient from study. Do meet criteria for dosing; administer study drug treatment.

ECGs to be performed at specified time point	Abnormality Noted	Dose Modification Guideline - At any time during a cycle of therapy (including intended day of dosing)
Dose modifications are based on local readings of the average QTcF* of triplicate ECGs. *QTcF: Heart rate corrected QT interval using the Fredericia formula: $QTcF = QT (msec) / \sqrt[3]{RR}(sec)$		

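### Exclusion 5 prints the square-root (Bazett) expression under the name QTcF, and Table 7-5's triplicate-average rules do not fit the single-ECG schedule

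*Combined protocol and SAP*

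**What the plan says.** **Formula.** Exclusion 5 (Section 6.1.2) rules out patients by "Screening ECG with a $QTcF > 470$ msec ($QTcF = QT/\sqrt{RR". Section 7.5.4 says the ECG machine's value is calculated "according to the Bazett formula ($QTcB = QT/\sqrt{RR", the same expression, and defines QTcF as QT over the cube root of RR. The Table 7-5 header repeats the cube root. Section 7.5.4 adds: "Any panobinostat dosing or withholding decisions will only be made after calculation of the QTcF". For the screening ECG, exclusion 5 says only: "If potassium or magnesium blood levels are below normal limits, consider repeating ECG after correction of these electrolytes". Baseline results "must be reviewed by the Principal Investigator prior to enrollment of that patient". The lowest eligible heart rate follows from "Bradycardia defined as $HR < 50$ bpm".

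**ECG schedule.**
- Table 7-5 lists three ECGs before and after panobinostat on cycle 1 days 1 and 5, and three before dosing on day 1 of later cycles. Dose changes rest on the average of the three. One trigger before dosing is a rise of more than 60 msec over an averaged baseline.
- Section 8 footnote 5 and the Table 9-1 rows ask for one ECG at screening, at each of the four cycle 1 time points, and before dosing on cycle 2 day 1. Section 9.1.6 makes the Section 8 time points the minimum.
- Section 7.4 makes an ECG mandatory only before cycle 2.
- The asterisk footnote to Table 8-1 bars any new cycle without an ECG in the preceding 24 hours.
- The note under Table 9-1 presumes monitoring over four cycles. Its footnote a sends the reader to a Table 6-7 for dose changes, but the table that holds them is 7-5.

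**The concern.** An eligibility limit should have one meaning. The name in exclusion 5 points to one correction and the expression beside it to another, and the two differ at every heart rate except 60 bpm. Section 7.5.4 requires the cube-root value before panobinostat is given or withheld; it does not mention eligibility. The repeat ECG that exclusion 5 suggests is for low electrolytes and would be judged by the same printed expression. The principal investigator's review could catch the slip, but exclusion 5 gives the reviewer the wrong formula.

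The ECG conflict matters because these readings decide holds, 5 mg panobinostat reductions and removal from study, in a trial whose primary objective is tolerability and safety. Phase II patients are treated until a discontinuation criterion is met (Section 5.2), so it needs to be clear whether an ECG is due from cycle 3 onward. It also needs to be clear whether one reading or a mean of three drives the decision.

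**Working it through.** **Inputs.** The 470 msec limit, the two formulas and the 50 bpm floor come from Sections 6.1.2 and 7.5.4. The other heart rates are illustrative. The plan gives no figure of its own to reproduce here.

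**Step 1, what the printed limit means on the cube-root scale.** With RR = 60/HR in seconds, set QT/RR^(1/2) = 470. Then QT = 470 × RR^(1/2), and the cube-root value is QT/RR^(1/3) = 470 × RR^(1/6). At 70 bpm, RR = 0.857, QT = 435.1 and the cube-root QTcF is 458.1.

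| HR (bpm) | RR (s) | Cube-root QTcF at the printed limit | Difference from 470 |
|---|---|---|---|
| 50 | 1.200 | 484.5 | +14.5 |
| 55 | 1.091 | 476.9 | +6.9 |
| 60 | 1.000 | 470.0 | 0 |
| 70 | 0.857 | 458.1 | −11.9 |
| 80 | 0.750 | 448.0 | −22.0 |
| 90 | 0.667 | 439.3 | −30.7 |
| 100 | 0.600 | 431.6 | −38.4 |

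Above 60 bpm the printed expression is stricter than a 470 msec QTcF limit; below 60 bpm it is more lenient.

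**Step 2, who could be affected.** A patient with cube-root QTcF q fails the printed limit above HR = 60 × (470/q)^6. That is 68.3 bpm for q = 460, 77.9 for 450, 89.1 for 440 and 102.3 for 430. Section 2 gives the phase I pre-treatment range as 378 to 430 msec, so even the highest value fails only above 102 bpm. Those patients had already passed screening, and screen failures are not reported.

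**Step 3, the lenient direction.** Before the first dose, Table 7-5 acts on "Average QTcF > 470 msec", on the cube-root scale. After correction and repeat ECGs the rule is: "Do not meet criteria again, discontinue patient from study". A patient admitted at 50 to 59 bpm with a value above 470 should be found there.

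**Step 4, ECG counts per patient, screening aside.** Cycle 1 has four time points (days 1 and 5, before and after dosing) and cycle 2 day 1 adds one. Through cycle 2 day 1 this gives 5 single ECGs under footnote 5 and Table 9-1, against 5 × 3 = 15 under Table 7-5. The number of time points over six cycles is:
- Footnote 5, Table 9-1 rows and Section 7.4: 4 + 1 = 5
- Table 9-1 note (four cycles): 4 + 3 = 7
- Asterisk footnote, and the timing in Table 7-5: 4 + 5 = 9

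**Step 5, the baseline.** Footnote 5 allows extra ECGs under 7.5.4 when prolongation prevents dosing or on clinical need. Those follow an abnormal reading. They cannot supply an averaged pre-dose baseline for a patient whose only cycle 1 day 1 pre-dose ECG was a single normal one.

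**The case against.** **The formula may be a reading artifact.** The difference is one small root index in a parenthesis. Loss of the index in PDF reading cannot be excluded. It is unlikely, because the index survives in Section 7.5.4 and throughout Table 7-5.

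**The operative word is QTcF.** The protocol defines that with the cube root, has trained nurses or the principal investigator calculate it, and applies 470 on that scale before the first dose. This stands. A reader might infer that the trial in fact excludes everyone above 458 at 70 bpm. The documents support only that a site could do so, by following the parenthesis over the label. A reader might also infer a safety gap at low heart rates; the cycle 1 day 1 check answers that.

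**Section 8 governs the schedule and Table 7-5 covers abnormal readings only.** Section 9.1.6 does make the Section 8 time points the minimum, and footnote 5, the Table 9-1 rows and Section 7.4 agree with one another. But Table 7-5 presents its triplicates as the ECGs due at set time points, before any abnormality is known, and its rules need averages that the schedule does not produce. The objection therefore narrows the conflict without removing it.

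**The size can be exaggerated.** Reading Table 7-5 as a routine schedule gives 12 + 3 × 5 = 27 ECGs per patient over six cycles, or 540 for 20 phase II patients, against 100 under footnote 5. That is the extreme reading, with an arbitrary six-cycle horizon. Nor does Table 7-5 ask for triplicates at screening, for which it has no row.

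**Conclusion.** Both inconsistencies hold and should be corrected.

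The formula error is conditional. If the printed expression is used, the limit is about 12 msec too strict at 70 bpm, 22 at 80 and 38 at 100, and 14.5 too lenient at 50. Wrongful exclusion is possible but probably rare. No safety harm is shown, because the lenient direction should be caught before dosing. This rests on the index being absent from the source document.

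The ECG conflict does not depend on the formula. Dose rules written for averages of three and an averaged baseline sit beside a schedule of single readings. The asterisk footnote agrees with Table 7-5 on timing but not with footnote 5, and the four-cycle note matches neither. No effect on a planned analysis is demonstrated; what is at stake is consistent dose and discontinuation decisions across patients.

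**What to change.** - In exclusion 5, print QTcF as QT over the cube root of RR, as in Section 7.5.4.
- Keep single ECGs for routine checks. Require triplicate confirmation before any hold, reduction or discontinuation when a single reading is above 470 msec on cycle 1 day 1 or, afterwards, at or above 481 msec or more than 60 msec above baseline.
- Name the cycle 1 day 1 reading that serves as baseline.
- Align the asterisk footnote, footnote 5, Section 7.4 and the Table 9-1 note on whether ECGs continue past cycle 2. The sponsor should choose the duration; this point does not ask for less monitoring.
- Correct the Table 6-7 reference to Table 7-5.

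The cost is amendment wording and a small number of repeat ECGs, which cannot be fully quantified. For the 60 msec trigger alone, assume a single-ECG SD of 10 to 15 msec (not from the documents), independent normal errors, a single-ECG baseline and a mean rise of 0.043 × 405 = 17.4 msec (Section 2). The false-trigger probability is the normal tail beyond (60 − 17.4)/(SD × √2): 0.0013 at SD 10 and 0.0223 at SD 15. Over 4 × 20 = 80 post-baseline readings through cycle 2 day 1, that is about 0.1 to 1.8 repeat triplicates. The 470 and 481 msec triggers and between-patient variation would add to this. The Section 2 input is itself soft: a 13% maximum rise from 430 gives at most 486 msec, yet the same section reports one value of 552.
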